#### 10:3 Sample size

The sample size is calculated to enable detection of a 0.75-point difference in change in SOFA-score after 7 days of treatment with 80% statistical power is based upon parametric statistics. In particular a limited effect during a short treatment period was taken into considerations. The choice of change in SOFA score was partly done on account that it can be assumed to be neutral to a non-identical The sample size of approximately 500 patients in each group are needed under these assumptions.

#### 10:4 Multi-centre

The major centres in the Scandinavian countries do not have more than approximately 100 patients that stay for more than 5 days in the ICU, therefor a multi-centre design of the study is necessary. It is also desirable that the study can be concluded within 18 months. It is also desirable that each centre participating contribute with not less than 25 patients. It is therefor

natural that this protocol is a multi-centre study in the Scandinavian countries. The plan is to recruit 500 patients in 10 centres in Sweden and 500 patients in 10 centres in Denmark, Finland and Norway.

#### 10:5 Statistical methods

Student's t-test will be used to compare the 2 groups when variables are normally distributed, this is expected to be the case for the change in SOFA score. For length of stay a rank-test will be used where survival is ranked higher than death and death after a long period of time is ranked higher than death after a short period of time. For mortality a Kaplan-Meyer plot and ?-analysis will be used.

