Another problem is how to define morbidity and mortality. The latter is easily defined although the ICU mortality may be influenced by different routines in individual centres. In addition the beneficial effects attributable to nutritional support may be extended also to the convalescence and rehabilitation period and therefore 6-months mortality is considered a more adequate measurer than in unit or in hospital mortality. Concerning morbidity it may be reflected in the SOFA-score, which take failure in several organs into account (38). As there is a close correlation between SOFA-score and mortality, it may be the best integrated measure of morbidity. Morbidity of clinical importance it may also be reflected in the length of ICU-stay. It is obvious that ICU-stay is variable inbetween units as much as it depends upon the pressure on available ICU-beds and the quality of the post-ICU care. Hospitals with step down units may have quite different routines from those hospitals that lack such a facility. Although there will be considerable differences between units, a block-randomisation may at least to some extent take care of these problems. Still definition of morbidity is problematic, and to choose a measure of morbidity as a primary endpoint must always include a number of compromises.

In addition a close record of the nutrition given is also necessary to verify that the intended treatment is actually received by the patients. The record should include the energy given as well as nitrogen content.

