## 4:2 Secondary objectives

The ICU mortality, the 6-months mortality, the length of ICU stay and the change in SOFAscore on day 10 of ICU stay as compared to the day starting nutritional treatment and glutamine supplementation will also be calculated.

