## 8:2 Secondary objectives

Mortality in the ICU and after discharge up to 6 months will be recorded and the cause of death will be registered. The difference in SOFA-score will also be calculated until day 10 of ICU stay according to the same procedure as for the primary objective under section 8:1. Length of ICU stay will also be recorded. If the patient is readmitted within 24 h after discharge the study continues. Readmission later than 24 h after discharge will not be recorded.

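### The length-of-stay rank test gives no order for survivors by ICU stay; completed in the likely way it is a composite of death and stay, so a significant result cannot be read as an effect on stay

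*Protocol*

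**What the plan says.** Section 4:2 lists the secondary objectives: "The ICU mortality, the 6-months mortality, the length of ICU stay and the change in SOFAscore on day 10 of ICU stay". Length of stay is thus a separate item from both mortality outcomes. Section 3 explains why it is of interest: "Morbidity of clinical importance it may also be reflected in the length of ICU-stay".

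Section 8:2 adds only "Length of ICU stay will also be recorded", with a rule for readmission within 24 hours. Section 10:2, on the statistics for secondary objectives, covers mortality and the SOFA change and does not mention length of stay.

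The analysis rule stands in section 10:5 alone: "For length of stay a rank-test will be used where survival is ranked higher than death and death after a long period of time is" placed above an early death. The second part of the rule, in full, is "death after a long period of time is ranked higher than death after a short period of time". The next sentence gives mortality its own analysis: "For mortality a Kaplan-Meyer plot and" a chi-square analysis.

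**The concern.** The two ordering rules use two facts about a patient: alive or dead, and the time of death if dead. Neither places one survivor relative to another. The only stated direction for time applies to deaths, where longer is better. For survivors a shorter stay would normally count as better, so the direction cannot simply be carried over and has to be written down.

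Two errors are possible in the report. A difference in deaths, already tested under mortality, could appear again under the label of length of stay. And a real shortening of stay could be missed, either because survivors were tied or because a mortality difference in the other direction offset it. Either way the length-of-stay objective in 4:2 would get a conclusion that the test does not support.

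**Working it through.** **Inputs.** From the protocol: 500 patients per group (6:5) and the two ordering rules (10:5). The protocol gives no mortality rate, no stay distribution and no planned effect for length of stay, so there is no stated figure to reproduce. Assumed: ICU mortality of 6% to 30%; log-normal stay with median 8 days, log-SD 0.7 and minimum 3 days; two-sided 5%; death independent of stay; survival taken as survival to ICU discharge, which 10:5 does not specify.

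**Two readings.**
- Literal: all survivors tied above all deaths, deaths ordered by time.
- Completed: survivors above all deaths, shorter stay better, deaths ordered by time.

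**Step 1: what the rank test measures.** Let m0 and m1 be mortality on placebo and glutamine. Let q be the probability that a glutamine survivor has a shorter stay than a placebo survivor. Under the completed reading, the probability that a glutamine patient ranks above a placebo patient is

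θ = (1 − m1)·m0 + (1 − m1)(1 − m0)·q + 0.5·m0·m1.

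Its null standard error with 500 per arm is √(1001 / (12 × 500 × 500)) = 0.01827.

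**Step 2: mortality differs, stay unchanged (q = 0.5).** Then θ − 0.5 = (m0 − m1)/2, whatever the stay distribution.
- 20% vs 15%: 0.025 / 0.01827 = 1.37; rejection Φ(1.37 − 1.96) ≈ 28%.
- 20% vs 13%: 0.035 / 0.01827 = 1.92; rejection ≈ 48%.
- 10% vs 6%: 0.020 / 0.01827 = 1.09; rejection ≈ 19%.

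Under the literal reading θ is the same, but ties shrink the standard error by √(1 − s³), where s is the overall proportion surviving. For 20% vs 15%, s = 0.825 and the standard error is 0.01827 × √(1 − 0.5615) = 0.01210. Then 0.025 / 0.01210 = 2.07 and rejection is about 54%.

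**Step 3: stay 15% shorter, mortality equal.** Ignoring the 3-day minimum, q = Φ(0.1625 / (0.7 × √2)) = 0.565, where 0.1625 = −ln 0.85. Under the literal reading θ = 0.5, so the test rejects at its 5% error rate. Under the completed reading θ − 0.5 = (1 − m)² × 0.0652:
- m = 10%: 0.0528, rejection ≈ 82%.
- m = 20%: 0.0417, rejection ≈ 63%.
- m = 30%: 0.0319, rejection ≈ 42%.

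**Step 4: stay 15% shorter, mortality 20% vs 25%.** θ = 0.75 × 0.20 + 0.75 × 0.80 × 0.5652 + 0.5 × 0.20 × 0.25 = 0.514. Then 0.0141 / 0.01827 = 0.77, and rejection is about 12%.

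**Step 5: simulation.** Repeated runs of 2,000 replicates with tie-corrected Mann-Whitney tests agree with these figures:

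| Scenario | Literal | Completed |
|---|---|---|
| Stay 15% shorter, mortality 10% in both arms | 4–5% | 81–83% |
| Same, 20% in both | 5–6% | 62–63% |
| Same, 30% in both | 5% | 40–42% |
| Stay unchanged, mortality 20% vs 15% | 53–56% | 26–28% |
| Stay unchanged, mortality 20% vs 13% | 84–86% | 46–51% |
| Stay 15% shorter, mortality 20% vs 25% | 46–49% | 11–13% |

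In the last row the literal test rejects because of the excess deaths, that is, against glutamine, although stay is shorter on glutamine. With a log-SD of 0.8 and a 20% shorter stay the pattern is the same: the literal test stays near 5%, and the completed test has about 93%, 79% and 55% power at 10%, 20% and 30% mortality.

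**Step 6: the obvious alternative.** Gray's test on live discharge, with ICU death as a competing event, was simulated under the same assumptions without censoring. With stay unchanged it rejects 45–47% at mortality 20% vs 15% and 74–75% at 20% vs 13%. With stay 15% shorter and equal mortality of 10%, 20% and 30%, its power is about 47–49%, 27–28% and 16–18%. It depends more on mortality and less on stay than the completed rank test.

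**The case against.** The strongest reply is that section 10:5 names length of stay as the variable to be ranked, and that the two clauses only say where deaths go. On that reading it is an ordinary worst-rank analysis, and a sound one, because it stops an early death from counting as a favourable short stay. The missing direction is one clause that an analysis plan could supply, and mortality is reported separately, so a reader can see whether deaths drive the result.

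Much of this stands. A reader might infer from 10:5 that survivors are deliberately left unranked and that the test can never detect a difference in stay. The protocol does not say so: it is silent on the order of survivors and does not declare them tied. The 5% power, and the rejection rates above 50% for mortality alone, belong to the literal reading only. Nor does the protocol say that a long stay counts as good in a survivor. Placing deaths lowest is legitimate.

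It does not settle the matter. The completed ranking is still a composite, and the protocol labels it as the test of length of stay. Reporting mortality beside it helps only if the report treats the rank test as a composite. An analysis plan that follows 10:5 would inherit the label.

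A comparison of stay in survivors alone would show higher power (about 83% to 93% for the 15% reduction), but it conditions on an outcome after randomisation. It looks clean here only because death was simulated as independent of stay. It is a benchmark, not a remedy.

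**Conclusion.** The point holds in limited form. Section 10:5 fixes an order for survival against death and for time to death, and leaves survivors without an order or a direction. Read literally, the test has no power for stay. Read in the likely intended way, it has useful power for stay when mortality is equal. It also rejects at several times the nominal 5% when only mortality differs (about 27% at 20% vs 15%) and largely loses a 15% shorter stay when mortality moves the other way (about 11% at 20% vs 25%). On either reading, a significant result is not evidence of an effect on length of stay.

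The percentages rest on assumed mortality and, where stay changes, on an assumed log-normal stay. The mortality-only figures do not depend on the stay distribution. The finding concerns one of several secondary endpoints; the SOFA comparison and the mortality analyses are untouched.

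**What to change.** Reword the sentence in 10:5 to state that:

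1. survivors rank above all deaths, with a shorter ICU stay better;
2. deaths are ranked by time to death, later being better;
3. the test is a composite of ICU death and ICU stay, reported under that name;
4. no conclusion on length of stay is drawn from it alone. It is read beside the mortality result and a descriptive report of ICU stay by arm and survival status.

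Cumulative incidence of live discharge by arm may be shown as description. Gray's test should not replace the rank test, for the reason in step 6.

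The cost is a wording change and one descriptive table. Discharge date and route of discharge, including death, are already on the report form (19:4), so no extra patients or data are needed. The small downside is that this secondary endpoint can then claim only a composite effect.

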## 10:6 Subject classification

All patients who are eligible for the study are registered and if they are not randomised the reason is noted. All patients that are randomised are registered as randomised and as included if treatment is started. For patients who are randomised but not included the reason is noted. Patients who are randomised and have received treatment will be classified as withdrawals. Patients may withdraw from the trial at their own request or at the discretion of the investigator. Patients treated for less than 3 days (3 treatment periods) will also be classified as withdrawals. Patients with failure of treatment on two consecutive days will also be withdrawn from the study. A minimum of 3 treatment periods on consecutive days will be necessary for evaluation. Analyses of the results will be made on the basis of included patients as well as on the basis of "intention to treat" and "screened patients". "Intention to treat" meaning all patients randomised, including those not given 3 days of treatment depending upon death, discharge or discontinuation of other reasons. "Screened patients" meaning all patients possible to include.

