## 8. Efficacy assessment

Each day of the study following things will be performed:

a) study drug (glutamine or placebo) will be given intravenously during 12 h.

b) volume of infused solution and time interval of infusion will be registered.

c) total amount of nutrition during 24 h will be recorded.

d) SOFA score will be calculated.

End of ICU-stay will be recorded and as well as the route of discharge. If the patient is moved to another intensive care unit, the patient leaves the study. Still if the patient is treated more than 3 days, he is included and evaluated in the study although the ICU-stay is prolonged in another unit and patient during that time does not receive any controlled treatment. Provision of nutrition after ICU-stay (or after readmission to ICU) will not be recorded. If patient is readmitted to ICU within 24 h study protocol is continued. If patient is readmitted to ICU after more than 24 h the patient will not be included. Patient will not be included again in the study and the second (or consecutive) stay will not be recorded as ICU-stay in the protocol.

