#### 8:1 Primary objective

The difference in SOFA-score will be calculated from the day starting nutritional treatment as well as glutamine supplementation until day 7 of ICU stay. For patients discharged or dead before day 7, the SOFA score on the day of discharge/death will substitute the latter score. In case of restrictions in treatment, SOFA score will be recorded as long as the nutrition of the patient is maintained.

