#### **10. Statistics**

The study is designed with one primary endpoint as the primary objective and several secondary endpoints as secondary objective. The statistical power calculation to determine the sample size is performed for the primary endpoint. Parametric and non-parametric statistics will be used depending on whether the parameters are normally distributed or not. As 3 days of treatment is an inclusion criteria all calculation will be made on included as well as randomised patients (intention to treat)

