### 10:7 Drop-outs and Missing Data

Drop-outs before day 7 of ICU stay will be considered as withdrawals. Drop-outs after that day will be evaluated in the primary outcome variable, and the same goes for day 10. For evaluation in length of stay and mortality, drop-out will be considered as withdrawals. Missing data will be considered as non-existent.

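### Two consecutive days of treatment failure remove a patient from the study, leaving no SOFA score provided for in the promised intention-to-treat comparison

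*Protocol*

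**What the plan says.** Protocol section 10:6 sets the rule: "Patients with failure of treatment on two consecutive days will also be withdrawn from the study". The discharge part of the report form (19:4) agrees with it, listing failed administration of the drug as a drop-out reason beside withdrawn consent.

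The other relevant provisions are:

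- **SOFA schedule (section 8).** The daily tasks, SOFA among them, are introduced by "Each day of the study following things will be performed".
- **Data at withdrawal (6:4).** When participation is terminated by the investigator or at the patient's or relative's request, only comments or complaints and the reason are recorded.
- **Substitution (8:1).** "For patients discharged or dead before day 7, the SOFA score on the day of discharge/death will substitute the latter score". Section 8:2 applies the same procedure to day 10.
- **Transfers (section 8).** A patient moved to another ICU after more than 3 days of treatment leaves the study, yet "he is included and evaluated in the study although the ICU-stay is prolonged in another unit".
- **Drop-outs and missing data (10:7).** "Drop-outs before day 7 of ICU stay will be considered as withdrawals", and "Missing data will be considered as non-existent".
- **Analysis sets.** Section 10 says that "all calculation will be made on included as well as randomised patients (intention to treat". Section 10:6 defines intention to treat as "meaning all patients randomised, including those not given 3 days of treatment", whether the cause was death, discharge or some other discontinuation.

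**The concern.** The protocol does not separate stopping the study drug from leaving the study. A patient whose infusion fails on two consecutive days is still in the ICU, still has the routine measurements behind a SOFA score, and has not refused data collection. Under 10:6 that patient is nevertheless withdrawn, and nothing provides for scoring afterwards.

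The primary endpoint would then be missing because of something that happened to treatment after randomisation. If the arms differ in how often this happens, or in the condition of the patients it happens to, the intention-to-treat comparison is biased. If they do not differ, the cost is fewer patients and some power.

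The gap is confined to SOFA. Deaths are reported for all randomised patients (9:2), 6-month mortality comes from a public register (10:2), and discharge is recorded on form 19:4. Patients who drop out after day 7 are evaluated for the primary endpoint (10:7).

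**Working it through.** **1. Tracing one patient through the text.** Take a randomised patient, still in the ICU before day 7, with two consecutive failed treatment days.

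- Under 10:6 the patient is withdrawn from the study.
- Section 8 schedules SOFA on days of the study, and no passage extends it beyond withdrawal. Scoring is not forbidden; it is simply not provided for.
- 8:1 supplies a substitute only on discharge or death before day 7, so a patient who stays in the ICU gets none.
- 10:7 makes the patient a withdrawal and leaves the missing value out.
- Sections 10 and 10:6 count the patient in the intention-to-treat set.

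The last two steps cannot both be carried out in full. The transfer rule in section 8 shows that the authors could keep a patient evaluable after controlled treatment ends; drug failure has no counterpart.

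**2. When a score is lost.** Let the drug start on ICU day s, and let *k* doses be given before two failed days. Withdrawal then falls at the end of day s + k + 1.

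| Start day s | Doses k | Withdrawn at end of day | Day 7 scored? | Day 10 scored? |
|---|---|---|---|---|
| 3 | 3 | 7 | yes | no |
| 2 | 3 | 6 | no | no |
| 3 | 1 | 5 | no | no |

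Day 7 is exposed mainly for patients whose drug fails early. They belong to the intention-to-treat set. Day 10 is exposed in every row.

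**3. Possible bias (all inputs assumed).** Let p be the share of an arm with no score, and d the amount by which the missing changes are worse than the observed ones. The arm's full mean is its observed mean plus p × d. With the same d in both arms, the between-arm difference shifts by (p1 − p0) × d.

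| Imbalance p1 − p0 | d = 2 points | d = 4 points | Share of 0.75 |
|---|---|---|---|
| 0 | 0 | 0 | 0% |
| 0.02 | 0.04 | 0.08 | 5% to 11% |
| 0.05 | 0.10 | 0.20 | 13% to 27% |

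**4. Power with no imbalance.** Section 10:3 gives about 500 per group, a 0.75-point difference and 80% power, but no standard deviation or significance level. The figure of 500 therefore cannot be reproduced independently. Assuming a two-sided 5% level and ignoring the interim adjustment that 10:1 mentions without specifying, the implied standard deviation is

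SD = 0.75 × √(500/2) / (1.960 + 0.842) = 4.23.

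With that SD:

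- 5% lost: 475 per arm (950 in total), power 78.0%.
- 10% lost: 450 per arm (900 in total), power 75.7%.

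**The case against.** The best case on the other side has four parts.

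*Withdrawal may be only a label.* The sentence stands under subject classification, next to one that classifies patients treated for less than 3 days as withdrawals, and the same section returns such patients to the intention-to-treat set. But the neighbouring sentence says classified, whereas this one says withdrawn from the study. Membership of the analysis set also does not create a score.

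*Few day-7 scores are at risk.* Section 4:1 considers only patients treated for at least 3 days, and screening is usually in the first 2 ICU days. For a patient with three doses starting on ICU day 3, withdrawal comes no earlier than day 7. This stands for the analysis of included patients, where the day-7 exposure is narrow. It does not cover early failures in the intention-to-treat set, or day 10. It also depends on counting ICU days; the Summary and 10:3 speak of 7 days of treatment, and on that count three doses and two failures end on day 5.

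*The event may be rare and balanced.* The infusion can go through a central or a peripheral line (section 7), and the placebo looks the same (5:3). This is fair. The imbalances above are assumptions, and the true one may be small.

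*Existing provisions may suffice.* 8:1 continues SOFA under restrictions in treatment while nutrition is maintained. That reads most naturally as limits on the level of care, and it mentions neither failed drug days nor withdrawn patients. It is true that a drug-stop date could be derived from the daily drug record, and that the form as reproduced is weak evidence about what is collected daily. Neither point supplies a rule for scoring after withdrawal.

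**Conclusion.** The concern holds. As written, the protocol withdraws patients for drug failure and provides no SOFA score for those who remain in the ICU before day 7 or day 10, while promising a comparison of all randomised patients. That comparison cannot be done in full by following the text.

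The conclusion rests on the wording alone. Its size is unknown: under the assumptions shown, it ranges from no bias and a loss of about 2 to 4 points of power to a shift of up to 0.20 points, about a quarter of the target difference. Day 7 is affected mainly through early failures, and day 10 more widely. An analysis plan could choose an imputation method but could not recover scores that were never recorded. The point should be fixed; confidence is medium, because the gap in the text is clear and only its effect is uncertain.

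**What to change.** - In 10:6, 6:4 and form 19:4, separate two statuses: study drug stopped (with date) and withdrawn from the study. Failed drug administration, or an investigator's decision to stop the drug, leads only to the first.
- For these patients, continue daily SOFA, nutrition and discharge recording until ICU discharge, with the 8:1 substitution rule applying as for everyone else. SOFA is the essential part.
- End recording only if the patient or relative refuses further data collection.
- State that these patients enter the intention-to-treat analysis with their observed scores. The analysis of included patients may still leave them out.

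The cost is protocol wording, one dated form field, and a few extra daily SOFA and nutrition entries per affected patient.
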